POPULATION CONCERNED:	
Criteria for inclusion:
 
 
• Male or female patient 18 years of age or older;
 
• Patient with Philadelphia chromosome positive or negative CML, or BCR-ABL positive, chronic, accelerated or blast phase;
 
• Patient resistant or intolerant to previous therapy with a TKI for CP, AP or BP CML other than bosutinib;
 
• Patient initiating bosutinib for treatment of CP, AP or BP Ph+/- CML, at the end of the inclusion visit or during the month preceding it;
 
• Patient who has been informed that a method of contraception must be used if a risk of pregnancy exists;
 
• Patient who has been informed about the study and who signed his or her consent form.
 
 
Criteria for non-inclusion:
 
 
• Patient with Philadelphia chromosome
 

	
negative CML, BCR-ABL negative chronic, accelerated or blast phase CML.
 
 
• Patient recently diagnosed with CML and who has not received previous treatment with TKI;
 
• Patient currently treated with a treatment other than bosutinib
 
• Patient of childbearing potential not using a method of contraception;
 
• Patient treated in the setting of an interventional study for another disease (outside of follow-up period);
 
• Patient who refuses computer processing of his/her medical data.
 

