
ORIGIN AND NATURE OF DATA COLLECTED
	
Patients will undergo collection of medical data indirectly by name at inclusion and during follow-up. Data collection will involve the following information:
 
 
- Compliance with criteria for inclusion and non-inclusion
 
- Demographic characteristics (year of birth, gender, weight, height, ECOG performance status)
 
- Description of CML (date of diagnosis and phase of CML at time of diagnosis, tests performed for diagnosis)
 
- History of therapeutic management: Descriptions of previous treatments of CML (type, dose, dosage, duration; better response to previous treatment; reasons for change in lines of treatment; type and grade of AEs which resulted in change of the previous line of treatment, better response obtained)
 
- Characteristics of patients at time of initiation of treatment with bosutinib: comorbidities and previous conditions, performance status, concomitant treatments
 
- Biochemistry and hematological assessments (at time of inclusion and follow-up)
 
- Description of CML at time of initiation of bosutinib (phase at initiation, responses to treatments and types of tests performed)
 
- Description of initiation of treatment with bosutinib (date of initiation, dose, dosage)
 
- Description of changes to treatments (bosutinib: changes to dose or dosage, temporary or permanent discontinuation of treatment; change to concomitant treatments)
 
- Safety and tolerability and management of toxicities related to bosutinib (concomitant treatments, additional corrective medical measures)
 

	
 
- Hematological, cytogenetic and molecular tests performed for monitoring of response to treatment
 
- Compliance with treatment
 
- Quality of life
 

Number of patients	
Since CML is a rare disease, a minimum number of patients is not expected. Therefore, in this context about 100 patients included in the study appears to be a reasonable objective, which will make it possible to have acceptable precision for estimates measured.

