### 9.2.1. Criteria for inclusion

Patients must satisfy all of the following criteria for inclusion in order to be eligible.

- Male or female patient 18 years of age or older;
- Patient with BCR-ABL Philadelphia chromosome positive or negative CML, in chronic, accelerated or blast phase;
- Patient resistant or intolerant to previous therapy with TKI for CP, AP or CB CML other than bosutinib;
- Patient initiating treatment with bosutinib for treatment of CP, AP or BP phase Ph+ / - CML at the end of the inclusion visit or during the one month prior to it;
- Patient who has been informed that a method of contraception must be used if a risk of pregnancy exists.
- Patients who have been informed about the study and who signed the informed consent form.

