#### **9.4.1.6. Measurement of quality of life**

Patient quality of life depends on treatments received and on complications encountered. It will be measured at the inclusion visit and at certain follow-up visits (M3, M6, M12, M18, M24, M36), by completion of a standardized questionnaire and validated in French FACT-leu (Functional Assessment of Cancer-Therapy-Leukemia, version 4 November 2007) in paper format for all patients in the study (Annex 3).

The FACT-leu questionnaire is a 44-item questionnaire with 5 modalities ranging from 0 (“not at all”) to 4 (“enormously”), evaluating 5 major dimensions of quality of life in the last 7 days: physical well-being (7 questions, score of 0 to 28), social/familial well-being (7 questions, score of 0 to 28), emotional well-being (6 questions, score of 0 to 24), functional well-being (7 questions, score of 0 to 28), and other subjects of concern (17 specific questions on leukemia, score of 0 to 68). A total score (of 0 to 176) can be calculated; a high score reflects good quality of life [24].

This questionnaire will be returned by the patient to the participating doctor at the end of the visit. All adverse events identified by the participating doctor via these questionnaire (e.g. “I have nausea” scored between 1 (a little) and 4 (enormously)) should be recorded in the study database and be reported to the Pfizer Pharmacovigilance department (*see 11 Erreur ! Source du renvoi introuvable.*

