#### **Modelling**

- Linear mixed model

PFIZER CONFIDENTIAL

CT24WI-GL02-RF01.1.0 *Model of non-interventional study protocol for study on collection of principal data*

15/08/2018

Page 34 of 79

Linear mixed models for repeated data will be used in the setting of analysis of continuous repeated data (longitudinal analyses). This approach will enable (1) to take into account all data from patients, and (2) to estimate at each measurement time the mean parameter on all of the patients, adjusted to the phase of CML and to treatment line. It will apply to analysis of biological and hematological parameters. The outcome in comparison to baseline (M0) will be estimated by appropriate contrasts.

- Logistical regression

Multivariate logistical regressions (binary variables) or polynomial (multi-categorical variables) will make it possible to estimate the association of qualitative parameters studied (e.g. response) and of explanatory variables (without notion of time). All models used will be adjusted to potential confounding factors or changes to effect.

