#### **Quality of life (FACT-leu version 4 – Specific questionnaire on leukemia)**

- Scores obtained based on the FACT-leu questionnaire will be calculated at each measurement time according to rules on calculation provided in Annex 3.5.
- The gain in quality of life, defined by the difference between the best score recorded for a patient and his baseline score, will be calculated.

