### **11.3. Period of reporting**

For each patient, the period of reporting of adverse events starts from the time when the patient received the first dose of the study medicinal product or starting from the date on which the patient provided his/her informed consent if he/she has already been exposed to the study medicinal product, and ends at the end of the observation period of the study, i.e. at least at the end of a period of 28 calendar days after the last administration of the study medicinal product (bosutinib); a report must be sent to the PFIZER Pharmacovigilance department or its certified representative for all types of adverse events listed in the abovementioned table and which occurred during this period. If the patient received the study medicinal product on the last day of the observational period, the period of reporting will be extended by 28 calendar days after the end of the observation period. Most often, the date of signature of the consent form corresponds to the date of inclusion of the patient in the study.

In some cases, there may be a difference between the date of signature of the consent form and date of inclusion in the study.

In the event that the patient provided his/her consent but was never included in the study (for example, a patient changed his / her mind on participation; screening failure), the period of reporting ends on the date of decision of non-inclusion of patient.

If the participating doctor becomes aware of a SAE that occurred at any time after the end of the observational period and that is considered related to the study medicinal product (bosutinib), this SAE must also be reported to the Pfizer Pharmacovigilance department.

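### Laboratory change is measured from the inclusion visit (M0), although bosutinib may start up to a month earlier, so for some patients the baseline can be an on-treatment value

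*Protocol*

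**What the plan says.** Protocol Section 9.7.1 (Modelling) plans linear mixed models for repeated continuous data. On scope it says: "It will apply to analysis of biological and hematological parameters". On the reference point it says: "The outcome in comparison to baseline (M0) will be estimated by appropriate contrasts".

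Table 4 in Section 9.4.1 places the inclusion visit at M0 and the first follow-up visit at M3. The Synopsis and Section 9.3 collect laboratory data at inclusion and at follow-up.

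Section 9.2.1 requires that bosutinib be started "at the end of the inclusion visit or during the one month prior to it"; the Synopsis has the same rule. Section 11.3 provides for this group as well, setting a separate start of adverse-event reporting for a patient "if he/she has already been exposed to the study medicinal product" when consent is given.

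For quality of life, Section 9.7.3 defines gain as "the difference between the best score recorded for a patient and his baseline score". Section 9.4.1.6 has FACT-leu first completed at the inclusion visit.

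In the same Section 9.7.3, time to response, progression-free survival and overall survival all run from the start of bosutinib. Section 9.3 lists the initiation date among the data collected.

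**The concern.** A change from baseline is meant to compare values on drug with values before drug. M0 meets that aim for a patient who starts at the end of the inclusion visit. It need not do so for a patient who started during the preceding month, whose M0 blood counts and biochemistry may already reflect treatment. The protocol neither asks for a pre-dose value in these patients nor separates them in the model, so the baseline mean mixes two quantities.

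At stake is the description of how laboratory parameters move under bosutinib, in a study designed as a post-authorization safety study with biological and hematological toxicity among its secondary objectives. Effects that appear within the first weeks are the ones most exposed to being absorbed into the baseline. The laboratory analysis also uses a different time origin from the response and survival analyses.

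**Working it through.** **Plan's own figure.** The protocol gives no figure on this point. Its only precision figure for a percentage (Section 9.5: about 100 patients, half-width at most 10% at a 50% rate) reproduces as 1.96 × √(0.5 × 0.5 / 100) = 0.098. Nothing below depends on it.

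**Inputs from the protocol.** Reference M0; M0 = inclusion visit; permitted start from one month before that visit to its end; first follow-up at about 3 months.

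**Inputs not in the protocol (assumed).** p = share of patients who started before M0, possible range 0 to 1; s = share of the later effect already present at M0 in those patients.

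**Formula.** Let μ be the pre-dose mean, d0 the mean drug effect at M0 in early starters, and dk the mean effect at follow-up visit k, taken as equal in early and later starters.

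- Expected mean at M0: μ + p × d0
- Expected mean at visit k: μ + dk
- M0 contrast: dk − p × d0 = dk × (1 − p × s), with s = d0/dk

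**Share of the true change that the M0 contrast recovers, 1 − p × s**

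| p | s = 0.25 | s = 0.50 | s = 0.75 | s = 1 |
|---|---|---|---|---|
| 0 | 1.00 | 1.00 | 1.00 | 1.00 |
| 0.25 | 0.94 | 0.88 | 0.81 | 0.75 |
| 0.50 | 0.88 | 0.75 | 0.63 | 0.50 |
| 1.00 | 0.75 | 0.50 | 0.25 | 0.00 |

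At p = 0.50 and s = 0.60, the hidden share is 0.50 × 0.60 = 0.30.

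**What s might be.** If starts are spread evenly over the 30 days before M0 and the effect builds exponentially, the mean s is 0.77, 0.59, 0.37 or 0.21 for assumed time constants of 7, 14, 30 or 60 days.

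**Check with a fitted model.** A random-intercept mixed model was fitted to simulated data: 4,000 patients; visits at 0, 3, 6 and 12 months; true change 1.0; 14-day time constant. With nobody starting early, the M3 contrast was 1.00. With p = 0.25, 0.50, 0.75 and 1 it was 0.88, 0.73, 0.57 and 0.41. Using s = 0.59, the formula gives 0.85, 0.71, 0.56 and 0.41, in agreement up to simulation error.

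**The direction is not guaranteed.** Take an early effect that has gone by the follow-up visit: dk = 0, d0 = −1, p = 0.50. The contrast is 0 − 0.50 × (−1) = +0.50, an apparent rise where the true change is nil. If the early effect is opposite in sign to the later one, the contrast overstates the change.

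**FACT-leu.** Gain is best score minus baseline score. Suppose early side effects lower the M0 score by d. If the best score comes from follow-up, the patient's gain rises by d. If M0 itself may count as the best score, gain rises by something between 0 and d. Either way it cannot fall, so the bias is upward, opposite to the laboratory case under steady onset.

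**The case against.** The strongest reply is that the reach of the M0 contrast is narrow, and most of this stands.

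- The primary results (Section 9.7.2) are percentages of patients with related adverse events and with permanent discontinuation after one. Laboratory toxicity (Section 9.7.3) is reported as percentages graded by CTCAE against normal limits. None of these uses M0. A reader might infer that the safety profile as a whole will look milder; the protocol does not support that.
- The model also yields a mean at each measurement time, and those means do not depend on which value is called baseline.
- The mixed model is stated for biological and hematological parameters only. A reader might infer that quality-of-life change is attenuated in the same way. It is analysed differently, and the likely bias there is upward.
- Patients who start at the end of the inclusion visit are unaffected, and they could be nearly all of the cohort.
- Laboratory values come from the medical dossier under routine care (Section 9.4.1). The case report form is a separate document and may accept a pre-dose result. Section 9.7 also lets the statistical analysis plan change non-primary analyses without an amendment.

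The last item stands only in part. The protocol does not leave the baseline open; it names M0. A later analysis plan can redefine baseline, but it cannot supply pre-dose values that nobody was asked to retrieve.

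It is also fair to object that dropping already-treated patients would shrink a cohort of about 100, select on route of entry and work against the model's stated aim of using every patient's data. The fix below therefore keeps them.

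**Conclusion.** The point holds as a defect in one secondary analysis. As written, the laboratory change contrasts pool pre-dose values with values that can be on-treatment. Under steady onset in one direction, the mean change is understated by p × s. With p and s both unknown, this runs from nothing (p near 0) to substantial, for example 30% at p = 50% and s = 60%. A reader might take that 30% as the expected size; it is an illustration only, because the protocol contains no basis for either input. Nor is understatement certain: a transient or opposite early effect can overstate the change or reverse its sign.

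FACT-leu gain is a separate and smaller matter: it may be inflated, on the condition that early side effects do lower an on-treatment M0 score.

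The primary adverse-event percentages and the CTCAE-graded percentages are untouched. The change is still worth making, because the affected patients can be identified from data already collected and the other time-based analyses already start from initiation.

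**What to change.** **Laboratory parameters**

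- Define baseline as the last routine value on or before the first bosutinib dose, taken from the medical dossier and recorded with its date.
- Count model time from the bosutinib initiation date, which is already collected.
- Where no pre-dose value exists, keep the patient's follow-up data in the model, do not treat M0 as that patient's baseline, and show this group separately.
- Report how many patients started before M0 and by how many days, so that p is known.

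**FACT-leu**

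- A pre-dose score cannot be recovered afterwards. Report gain separately for patients whose M0 form precedes the first dose and for the rest.

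**Cost.** One earlier routine result must be retrieved for each already-treated patient, and somewhat fewer patients will contribute to the change-from-baseline contrasts. No visit or test is added, so the study remains non-interventional.

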### **9.7.2. Analysis of the primary objectives**

The following parameters will be evaluated in order to respond to the primary objectives:

- The percent of patients presenting with adverse events considered related to bosutinib by the participating doctor will be described overall (all grades of seriousness combined, all types of events combined), depending on grade: 1, 2, 3 and 4 and grades 3/4, and by type of event.
- The percent of patients who permanently discontinued treatment with bosutinib following an AE considered related to bosutinib by the participating doctor will be described overall.

Analysis of the primary objectives will be detailed in the statistical analysis plan.

### **9.7.3. Analyses of secondary objectives**

#### **Safety profile with bosutinib:**

- The following percent will be described by System Organ Class (SOC) overall and according to grade of event whether it is considered as related to bosutinib or not (grade 1, 2, 3, 4, or grades 3/4):
  - o percent of patients presenting with AE that occurred with bosutinib
  - o percent of patients presenting with AE which required a change to treatment with bosutinib (a reduction of dose and/or temporary or permanent discontinuation)

- The percent of patients presenting with biological or hematological toxicities during treatment with bosutinib, whether considered related to bosutinib or not, will be described overall and according to grade of the event (grade 1, 2, 3, 4, or grade 3/4).  
The biological and hematological events will be estimated by the CTCAE v4.03 criteria of June 2010, with all values greater than the upper normal value, or lower than the lower normal value of the parameter considered.
- Measures taken to prevent AE will be described (supportive therapy, etc.).
- Biochemical and hematological parameters will be described in follow-up using a linear mixed model for repeated data.

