### 9.3. Variables

Patients will be identified indirectly via a unique number in the study (the centre no., patient no. pair).

The following “patient” data will be collected in the setting of the study at the usual consultation of patients in the centres.

Data	Role	Source
Compliance with criteria for inclusion and non-inclusion	Baseline characteristics	Inclusion visit
Demographic characteristics (year of birth, gender, weight, height, ECOG performance status)	Baseline characteristics	Inclusion visit
Diagnosis of CML (date of diagnosis, phase of CML at time of diagnosis, tests performed for diagnosis)	Baseline characteristics	Inclusion visit
Transcription of BCR-ABL gene at time of diagnosis	Baseline characteristics	Inclusion visit
Previous treatments of CML (type, dose, dosage, duration of previous treatment)	Baseline characteristics	Inclusion visit
Best response to previous treatments	Baseline characteristics	Inclusion visit
Reasons for change of previous treatments (if discontinuation for toxicity, description of the AE: type and grade)	Baseline characteristics	Inclusion visit
Phase of CML in the estimate of the participating doctor, at time of initiation of treatment with bosutinib	Baseline characteristics	Inclusion visit Follow-up visit
Evolution of mutational profile of BCR-ABL gene at time of initiation of treatment with bosutinib	Baseline characteristics	Inclusion visit Follow-up visit
Concomitant treatments at time of inclusion in the setting of management of CML	Baseline characteristics	Inclusion visit
Biological and hematological assessment data	Baseline characteristics Evaluation end point	Inclusion visit Follow-up visit
Hematological, cytogenetic and molecular response at time of inclusion and results	Baseline characteristics	Inclusion visit
Description of initiation of treatment with bosutinib (date of initiation, dose, dosage)	Baseline characteristics	Inclusion visit
Change to concomitant treatments in the setting of management of CML	Evaluation end point	Inclusion visit Follow-up visit
Description of treatment with bosutinib (changes to dose or dosage, temporary or permanent discontinuations of treatment)	Evaluation end point	Follow-up visit
Safety in treatment with bosutinib	Evaluation end point	Follow-up visit
Management of toxicities related to bosutinib (concomitant treatments, additional corrective medical measures)	Evaluation end point	Follow-up visit

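### The laboratory toxicity count in section 9.7.3 has no pre-bosutinib reference, so abnormalities already present before treatment are reported as toxicities on treatment

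*Protocol*

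**What the plan says.** Protocol section 9.7.3, under the safety profile, defines the endpoint as "The percent of patients presenting with biological or hematological toxicities during treatment with bosutinib, whether considered related to bosutinib or not". It is shown overall and by grade (1, 2, 3, 4 and 3/4 combined). The counting rule follows: "The biological and hematological events will be estimated by the CTCAE v4.03 criteria of June 2010", and the sentence continues "with all values greater than the upper normal value, or lower than the lower normal value of the parameter considered". It sets no condition on the value before treatment, on worsening or on confirmation.

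Laboratory values are collected at both ends. Section 9.3 lists "Biological and hematological assessment data" as both a baseline characteristic and an evaluation end point, recorded at the inclusion and follow-up visits. Baseline enters the analysis in one place, the linear mixed model of section 9.7.1: "The outcome in comparison to baseline (M0) will be estimated by appropriate contrasts".

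The population is defined in section 9.2.1: "Patient resistant or intolerant to previous therapy with TKI for CP, AP or CB CML other than bosutinib". The same section allows bosutinib to have been started up to one month before the inclusion visit.

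**The concern.** Section 8.2 asks which biological and hematological toxicities arose under bosutinib. The rule in section 9.7.3 answers a different question: which patients had an out-of-range value while taking it. In untreated healthy people the two might be close. Here every patient is resistant or intolerant to an earlier TKI and some are in advanced phase, so abnormal counts or chemistry at the start are to be expected. Such a patient contributes a toxicity without any change, and the grade recorded is the grade the patient arrived with.

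The protocol makes this distinction elsewhere. Section 11.5.1 treats an abnormal test as an adverse event only if it has symptoms, leads to investigation, intervention or a treatment change, or is judged to be one. The hospitalization rules in section 11.5.2 set apart admissions for laboratory abnormalities that predate treatment. The laboratory count has no such filter, so it can diverge from the adverse event tables for reasons unrelated to bosutinib. The study is designed as a post-authorization safety study, and readers will take this percentage as a safety result.

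**Working it through.** **The plan's own figure.** The protocol gives no expected value for the laboratory count. Its only figure for a percentage is the precision in section 9.5: half-width at most 10% with 100 patients and a 50% rate. This reproduces: 1.96 × √(0.5 × 0.5 / 100) = 9.8%.

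**Pre-existing abnormality.** Let *b* be the proportion abnormal before bosutinib and *i* the proportion of the remainder who become abnormal on treatment. Neither is in the protocol, so both are assumptions. Assume also that patients abnormal beforehand have at least one abnormal value on treatment and do not worsen.

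- Reported by the rule: *b* + (1 − *b*) × *i*
- Truly new: (1 − *b*) × *i*
- Excess: *b*

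| *b* | *i* | Reported | Truly new |
|---|---|---|---|
| 10% | 10% | 0.10 + 0.90 × 0.10 = 19% | 9% |
| 25% | 10% | 0.25 + 0.75 × 0.10 = 32.5% | 7.5% |
| 40% | 10% | 0.40 + 0.60 × 0.10 = 46% | 6% |
| 10% | 25% | 0.10 + 0.90 × 0.25 = 32.5% | 22.5% |
| 40% | 25% | 0.40 + 0.60 × 0.25 = 55% | 15% |

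The excess equals the baseline prevalence whatever the new-onset rate. At *b* = 10% it already matches the half-width the protocol accepts as sampling error. With *i* fixed at 10%, the reported figure rises as the truly new figure falls.

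**Chance values.** Take one parameter with no true change, a normal range covering the central 95% of values, and one test at each of the 12 quarterly visits in Table 4 (M3 to M36). With independent visits:

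- both directions counted: 1 − 0.95^12 = 46.0%
- one direction counted: 1 − 0.975^12 = 26.2%
- both directions, 8 visits: 1 − 0.95^8 = 33.7%; 4 visits: 1 − 0.95^4 = 18.5%

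A simulation with equal within-patient correlation, both directions counted unless stated, gives:

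| Correlation | Flagged by the rule | Flagged and normal at M0 | Flagged, one direction |
|---|---|---|---|
| 0 | 45.9% | 43.6% | 26.2% |
| 0.5 | 31.8% | 28.3% | 15.9% |
| 0.8 | 18.6% | 14.2% | 9.2% |

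The third column shows that requiring a normal baseline lowers chance flagging by only about 2 to 4 points. Values just outside a limit fall mainly in the any-grade and grade 1 rows, whereas pre-existing abnormality can enter any row.

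**Whether baseline is handled elsewhere.** The mixed model estimates mean change from M0. It leaves the classification of each patient unchanged, so it cannot correct a percentage of patients.

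**The case against.** The strongest reply is that this is a secondary, descriptive count, explicitly reported whether or not the doctor relates the event to bosutinib, and that section 9.7.3 defers detail on secondary objectives to the SAP, which may add a treatment-emergent rule. The endpoint is indeed secondary. But a label that disclaims causality does not separate new from old abnormalities, and the protocol has not left the rule open: it states which values count. If the SAP adds a baseline condition, the two texts should be aligned.

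Several stronger readings are tempting but not supported.

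- *The rule ignores the direction that CTCAE grades.* The same sentence applies CTCAE v4.03, and the closing reference to each parameter is more naturally read as the limit relevant to it. The one-direction chance figures then apply. The missing baseline is unaffected.
- *Inclusion values are collected and never used.* They are used in the mixed model; they are absent only from the categorical count.
- *The any-grade figure will approach 100%.* Five or ten parameters over 12 visits would give 1 − 0.95^60 = 95.4% or 1 − 0.95^120 = 99.8%, but only with independent visits, independent parameters, both directions counted and full exposure. The protocol supports none of these as a set. Section 7.3 cites about 20% stopping after an adverse event in Study 200, and the long-term visits in section 9.4.1.3 list only CML phase and management.
- *A baseline reference cures the chance problem.* The simulation shows that it removes little of it.

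It is also fair that the inclusion value is not always a pre-dose value, because bosutinib may have started up to a month earlier. The fix has to allow for that.

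**Conclusion.** The point holds for pre-existing abnormality. Followed as written, section 9.7.3 counts abnormalities that predate bosutinib as toxicities during treatment, in any grade including 3/4, which is not what section 8.2 sets out to measure. The excess equals the baseline prevalence, which the protocol does not give. At an assumed 10% to 40%, with 10% new onset among the rest, the report would read 19% to 46% against 9% to 6% new. Patients whose existing abnormality worsens would narrow that gap. Chance flagging is a lesser, separate issue: about 19% to 46% for one parameter over the full 12 visits if both directions count, less with one direction or shorter exposure, and mainly in the any-grade and grade 1 rows.

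A reader might infer that the primary results are compromised. They are not: both primary endpoints rest on adverse events that the doctor relates to bosutinib. The change is worth making because it is cheap and the percentage is hard to interpret without it.

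**What to change.** In section 9.7.3, define a laboratory toxicity as an on-treatment CTCAE grade worse than the grade of the last value before the first bosutinib dose. Where bosutinib was started before the inclusion visit, take that value from the medical dossier, which section 9.4.1 already names as the data source. If none exists, report the patient in a separate baseline-unknown row instead of treating the M0 value as pre-dose. Add a shift table of baseline grade by worst on-treatment grade, and keep the all-values count as a secondary listing.

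The cost is a reworded rule, one table, and some retrieval of pre-dose values for patients who started before inclusion. The denominator with a known baseline will be somewhat smaller. No additional visit or test is needed. The any-grade and grade 1 rows will still contain isolated chance values, and a footnote should say so.
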